7.6.2. Investigator's Global Assessment

The grades for the IGA are shown in [Table 4](#).

[figure not shown]
Table 4: Investigator's Global Assessment

Grade	Severity	Status
0	Clear	No inflammatory signs of AD
1	Almost clear	Just perceptible erythema and just perceptible papulation/infiltration
2	Mild disease	Mild erythema and mild papulation/infiltration
3	Moderate disease	Moderate erythema and moderate papulation/infiltration
4	Severe disease	Severe erythema and severe papulation/infiltration
5	Very severe disease	Severe erythema and severe papulation/infiltration with oozing/crusting

7.6.4. Itch Numerical Rating Scale

[figure not shown]
The Itch NRS is a daily patient-reported measure (24-hour recall) of itch intensity. Subjects will be asked to rate the itching severity because of their AD by selecting a number from 0 (no itch) to 10 (worst imaginable itch) that best describes their worst level of itching in the past 24 hours.

[figure not shown]
Subjects will be issued a hand-held device (eDiary) on which to record itch severity. The subject will be instructed to complete the eDiary each night beginning on the day of screening through treatment discontinuation. Subjects will bring the device to the study site at each study visit so that the device charging can be verified and accumulated data can be downloaded, as applicable. The device will then be returned to the subject for continued use each night. The subject will return the device and the docking station for the final time at the EOT visit so that the data can be archived. Detailed directions for the administration of the eDiary will be provided in the Study Reference Manual.

7.6.6. Photography

For each visit with photography (baseline and Week 4), photographs of the areas of AD [REDACTED] [REDACTED] will be obtained.

7.10. Other Study Procedures

7.10.1. Distribution of Subject Diaries

Starting at the Day 1 visit and each visit thereafter, a diary will be given to each subject in order to record use of the study product. The completed diary will be collected during the subject's visit. Qualified clinical staff will review the subjects' entries for compliance. Subjects who are noncompliant with either their study drug (defined as < 80% or > 120% compliant based on prescribed application regimen and weight of study drug tubes) will have their administration instructions reinforced by the investigator or a qualified designee. Subjects will be considered compliant with the treatment regimen if they apply at least 80% but no more than 120% of the expected applications during participation in the treatment phase of the study.

8. SAFETY MONITORING AND REPORTING

8.1. Adverse Events

8.1.1. Definitions

For the purposes of this Protocol, an AE is defined as any untoward medical occurrence associated with the use of a drug in humans, whether or not considered drug related, that occurs after a subject provides informed consent. Abnormal laboratory values or test results occurring after informed consent constitute AEs only if they induce clinical signs or symptoms, are considered clinically meaningful, require therapy (eg, hematologic abnormality that requires transfusion), or require changes in the study drug(s).

8.1.2. Reporting

Adverse events that begin or worsen after informed consent should be recorded on the Adverse Events form of the eCRF. Conditions that were already present at the time of informed consent should be recorded on the Medical History form in the eCRF. Monitoring for the occurrence of new AEs should be continued for at least 30 days after the last dose of study drug. Adverse events (including laboratory abnormalities that constitute AEs) should be described using a diagnosis whenever possible rather than by individual underlying signs and symptoms. When a clear diagnosis cannot be identified, each sign or symptom should be reported as a separate AE.

The severity of AEs will be assessed using CTCAE v4.03 Grades 1 through 4. The CTCAE v4.03 severity of Grade 5 will not be used; AEs resulting in death will be graded accordingly using Grades 1 through 4 and have the outcome noted as fatal. If an event is not classified by CTCAE, the severity of the AE will be graded according to the scale below to estimate the grade of severity:

Grade 1	Mild; asymptomatic or mild symptoms; clinical or diagnostic observations only; intervention not indicated.
Grade 2	Moderate; minimal, local, or noninvasive intervention indicated; limiting age-appropriate activities of daily living.
Grade 3	Severe or medically significant but not immediately life-threatening; hospitalization or prolongation of hospitalization indicated; disabling; limiting self-care activities of daily living.
Grade 4	Life-threatening consequences; urgent intervention indicated.

The occurrence of AEs should be sought by nondirective questioning of the subject during the screening process after signing the ICF and at each visit during the study. Adverse events may also be detected when they are volunteered by the subject during the screening process or between visits, or through physical examination, laboratory test, or other assessments. To the extent possible, each AE should be evaluated to determine:

- The severity grade (CTCAE Grade 1 to 4).
- Whether there is at least a reasonable possibility that the AE is related to the study treatment: suspected (yes) or not suspected (no).

- The start and end dates, unless unresolved at final follow-up.
- The action taken with regard to study drug.
- The event outcome (eg, not recovered/not resolved, recovered/resolved, recovering/resolving, recovered/resolved with sequelae, fatal, unknown).
- The seriousness, as per SAE definition provided in [Section 8.3.1](#).

Unlike routine safety assessments, SAEs are monitored continuously and have special reporting requirements (see [Section 8.3.2](#)).

All AEs should be treated appropriately. If an AE is treated with a concomitant medication or nondrug therapy, this action should be recorded on Adverse Event form and the treatment should be specified on the Prior/Concomitant Medications or Procedures and Non-Drug Therapy form in the eCRF.

Once an AE is detected, it should be followed until it has resolved or until it is judged to be permanent; assessment should be made at each visit (or more frequently if necessary) of any changes in severity, the suspected relationship to the study drug, the interventions required to treat the event, and the outcome.

When the severity of an AE changes over time for a reporting period (eg, between visits), each change in severity will be reported as a separate AE until the event resolves. For example, 2 separate AEs will be reported if a subject has Grade 1 diarrhea, meeting the definition of an AE that lasts for 3 days before worsening to a Grade 3 severity. The Grade 1 event will be reported as an AE with a start date equal to the day the event met the Grade 1 AE definition and a stop date equal to the day that the event increased in severity from Grade 1 to Grade 3. The Grade 3 event will also be reported as an AE, with the start date equal to the day the event changed in intensity from Grade 1 to Grade 3 and a stop date equal to the day that the event either changed severity again or resolved.

8.2. Laboratory Test Abnormalities

Laboratory abnormalities that constitute an AE in their own right (considered clinically meaningful, induce clinical signs or symptoms, require concomitant therapy, or require changes in study drug) should be recorded on the Adverse Event form in the eCRF. Whenever possible, a diagnosis rather than a symptom should be provided (eg, "anemia" instead of "low hemoglobin"). Laboratory abnormalities that meet the criteria for AEs should be followed until they have returned to normal or an adequate explanation of the abnormality is found. When an abnormal laboratory test result corresponds to a sign or symptom of a previously reported AE, it is not necessary to separately record the laboratory test result as an additional event.

Laboratory abnormalities that do not meet the definition of an AE should not be reported as AEs. A Grade 3 or 4 (severe) AE does not automatically indicate an SAE unless it meets the definition of serious, as defined in [Section 8.3.1](#). A dose modification for the laboratory abnormality may be required (see [Section 5.4](#)) and should not contribute to the designation of a laboratory test abnormality as an SAE.

8.3. Serious Adverse Events

8.3.1. Definitions

An SAE is defined as an event that meets at least 1 of the following criteria:

- Is fatal or life-threatening.
- Requires inpatient hospitalization or prolongation of existing hospitalization, unless hospitalization is a result of:
 - A routine treatment or monitoring of the studied indication not associated with any deterioration in condition.
 - An elective surgery or preplanned treatment for a pre-existing condition that is unrelated to the indication under study and has not worsened since signing the ICF.
 - A treatment on an emergency outpatient basis for an event not fulfilling any of the definitions of a SAE and not resulting in hospital admission.
 - Any social reasons and respite care, in the absence of any deterioration in the subject's general condition.
- Results in persistent or significant disability, incapacity, or a substantial disruption of a person's ability to conduct normal life functions.
- Constitutes a congenital anomaly or birth defect.
- Is considered to be an important medical event or a medically significant event that may not result in death, be immediately life-threatening, or require hospitalization but may be considered serious when, based on appropriate medical judgment, the event may jeopardize the subject or may require medical or surgical intervention to prevent 1 of the outcomes listed above.

8.3.2. Reporting

Every SAE, regardless of suspected causality (eg, relationship to study drug(s) or study procedure or disease progression), occurring after the subject has signed the ICF through the last study visit (or 30 days after the last dose of study drug, whichever is later) must be reported to the sponsor (or designee) within **24 hours** of learning of its occurrence, unless otherwise specified by the Protocol. Any SAEs occurring more than 30 days after the last dose of study drug should be reported to the sponsor or its designee only if the investigator suspects a causal relationship to the study drug.

Information about all SAEs is collected and recorded on the Adverse Event form of the eCRF. The investigator must assess and record the causal relationship of each SAE to the study treatment.

The investigator must also complete the Incyte Serious Adverse Event Report Form, in English, and send the completed and signed form to the sponsor or designee within 24 hours of becoming aware of the SAE. The investigator must provide a causality assessment, that is, assess whether there is at least a reasonable possibility that the SAE is related to the study treatment: suspected

(yes) or not suspected (no). Refer to the Incyte Reference Guide for Completing the Serious Adverse Event Report Form.

The contact information of the sponsor's study-specific representatives is listed in the investigator manual provided to each site. The original copy of the SAE Report Form and the confirmation sheet must be kept at the study site.

Investigational site personnel must report any new information regarding the SAE within 24 hours of becoming aware of the information in the same manner that the initial SAE Report Form was sent. Follow-up information is recorded on an amended or new SAE Report Form, with an indication that it is follow-up to the previously reported SAE and the date of the original report. The follow-up report should include information that was not provided on the previous SAE Report Form, such as the outcome of the event (eg, resolved or ongoing), treatment provided, action taken with study drug because of the SAE (eg, dose reduced, interrupted, or discontinued), or subject disposition (eg, continued or withdrew from study participation). Each recurrence, complication, or progression of the original event should be reported as follow-up to that event, regardless of when it occurs.

If the SAE is not documented in the IB for the study drug (new occurrence) and is thought to be related to the sponsor's study drug, the sponsor or its designee may urgently require further information from the investigator for reporting to health authorities. The sponsor or its designee may need to issue an Investigator Notification (IN) to inform all investigators involved in any study with the same drug that this SAE has been reported. Suspected Unexpected Serious Adverse Reactions (SUSARs) will be collected and reported to the competent authorities and relevant ethics committees in accordance with Directive 2001/20/EC, or as per national regulatory requirements in participating countries.

8.4. Emergency Unblinding of Treatment Assignment

The procedure for emergency unblinding is provided in the study reference manual. This option may be used ONLY if the subject's well-being requires the investigator to be aware of the subject's treatment assignment.

The investigator should make every effort to contact the sponsor's (or its designee's) clinical research physician or medical monitor before unblinding a subject's treatment assignment; however, this is not mandatory. If a subject's treatment assignment is unblinded, the sponsor or its designee must be notified immediately by telephone.

If an investigator, site personnel performing assessments, or subject is unblinded, the subject must be withdrawn from the study treatment. In cases where there are ethical reasons to have the subject remain in the study, the investigator must obtain specific approval from the sponsor's (or its designee's) clinical research physician or medical monitor for the subject to continue in the study.

8.5. Pregnancy

Pregnancy, in and of itself, is not regarded as an AE unless there is suspicion that study drug may have interfered with the effectiveness of a contraceptive medication or method. When a pregnancy has been confirmed in a subject during maternal or paternal exposure to study drug, the following procedures should be followed in order to ensure subject safety:

- The study drug must be discontinued immediately (female subjects only; see [Section 5.4](#) for the maximum permitted duration of study drug interruption).
- The investigator must complete and submit the Incyte Clinical Trial Pregnancy form to the sponsor or its designee within **24 hours** of learning of the pregnancy.

Data on fetal outcome and breastfeeding are collected for regulatory reporting and drug safety evaluation. Follow-up should be conducted for each pregnancy to determine outcome, including spontaneous or voluntary termination, details of the birth, and the presence or absence of any birth defects, congenital abnormalities, or maternal and/or newborn complications, by following until the first well-baby visit. Pregnancy should be recorded on a Clinical Trial Pregnancy form and reported by the investigator to the sponsor or its designee. Pregnancy follow-up information should be recorded on the same form and should include an assessment of the possible causal relationship to the sponsor's study drug to any pregnancy outcome, as well as follow-up to the first well-baby visit or the duration specified in local regulations, whichever is later. Refer to the Incyte Reference Guide for Completing the Clinical Trial Pregnancy Form.

Any SAE occurring during pregnancy must be recorded on the SAE report form and submitted to the sponsor or designee.

8.6. Warnings and Precautions

Special warnings or precautions for the study drug, derived from safety information collected by the sponsor or its designee, are presented in the Investigator's Brochure ([IB](#)). Additional safety information collected between IB updates will be communicated in the form of Investigator Notifications (INs). Any important new safety information should be discussed with the subject during the study, as necessary. If new significant risks are identified, they will be added to the ICF.

8.7. Data Monitoring Committee

No external data monitoring committee will be used; however, an internal data monitoring committee will examine the interim analysis.

8.8. Product Complaints

The sponsor collects product complaints on study drugs and drug delivery systems used in clinical studies in order to ensure the safety of study participants, monitor quality, and facilitate process and product improvements.

All product complaints associated with material packaged, labeled, and released by the sponsor or its designee will be reported to the sponsor. All product complaints associated with other study material will be reported directly to the respective manufacturer.

The investigator or his/her designee is responsible for reporting a complete description of the product complaint via email or other written communication to the sponsor contact or respective manufacturer as noted in the packaging information. Any AE associated with a product complaint should be reported as described in [Section 8.1.2](#) of this Protocol.

If the investigator is asked to return the product for investigation, he/she will return a copy of the product complaint communication with the product.

[figure not shown]
9. STATISTICS

9.1. Study Populations

The intent-to-treat (ITT) population includes all randomized subjects. Treatment groups for this population will be defined according to the treatment assignment at randomization.

The per protocol population includes randomized subjects who are considered to be sufficiently compliant with the Protocol.

The safety evaluable population includes all subjects who applied at least 1 dose of study drug. Treatment groups for this population will be determined according to the actual treatment the subject received on Day 1.

9.2. Selection of Sample Size

The assumptions in [Table 5](#) were used for the percentage change from baseline in EASI scores at Week 4.

Table 5: Assumed Percentage Change From Baseline in EASI at Week 4

Treatment	Percentage Change
Vehicle	30%
Triamcinolone 0.1% (active control)	50%
INCB018424 1.5% BID	75%
INCB018424 1.5% QD	65%
INCB018424 0.5% QD	50%
INCB018424 0.15% QD	30%

The standard deviation was assumed to be 0.13 (13%). These assumptions were based on the review of a historical clinical study in AD ([Beck et al 2014](#)).

In order to provide a large safety database and to provided adequate power for efficacy variables, the total sample size for the study is 300 subjects randomized in a 1:1:1:1:1:1 ratio (stratified by baseline EASI score) to INCB018424 1.5% BID, INCB018424 1.5% QD, INCB018424 0.5% QD, INCB018424 0.15% QD, triamcinolone (active control), and vehicle.

9.2.1. Graphical Procedure

A graphical procedure with gatekeeping testing strategy for the primary and key secondary analyses will be implemented. A family of 7 elementary hypotheses, corresponding to treatment comparison between each active dose group to vehicle or triamcinolone is evaluated in [Figure 3](#) based on the percentage change from baseline to Week 4 of EASI score.

[figure not shown]
The primary endpoint will test the superiority of INCB018424 1.5% BID compared with vehicle. The key secondary endpoint has 2 branches. Branch 1 will test whether:

- INCB018424 1.5% BID is noninferior to triamcinolone (active control)
- INCB018424 1.5% QD is noninferior to triamcinolone (active control)
- INCB018424 1.5% BID is superior to triamcinolone (active control)
- INCB018424 1.5% QD is superior to triamcinolone (active control)

Branch 2 will test whether:

- INCB018424 1.5% QD is superior to vehicle
- INCB018424 0.5% QD is superior to vehicle

Figure 3: Illustration of the Statistical Treatment Comparisons

AC = active control; s = superiority; ni = noninferiority; V = vehicle.

9.2.1.1. Primary Analysis

The primary alternative hypothesis (superiority of INCB018424 1.5% BID compared with vehicle) will be tested at a 2-sided $\alpha = 0.05$ level. The test on the primary endpoint will be used

as a gatekeeper for 6 statistical tests on secondary endpoints that will be grouped into 2 parallel branches (see [Figure 3](#)). The first branch (Branch 1) includes tests of INCB018424 versus triamcinolone. The second branch (Branch 2) includes tests of INCB018424 versus vehicle, as visualized in [Figure 3](#). The initial allocation of the overall significance level to Branch 1 and Branch 2 is three-fifths and two-fifths, respectively. The weights of the level to be passed on if 1 hypothesis is rejected are specified in [Figure 3](#).

9.2.1.2. Secondary Analysis

9.2.1.2.1. Tests in Branch 1

- **Step 1:** The first alternative hypothesis (noninferiority of INCB018424 1.5% BID compared with triamcinolone) will be tested at a 2-sided $\alpha = 0.03$ level if the primary test is significant. If the first alternative hypothesis is established, then hypotheses in Step 2 will be tested at an overall error rate of 0.03.
- **Step 2:** If Step 1 is established, then a superiority test of INCB018424 1.5% BID compared with triamcinolone and noninferiority test of INCB018424 1.5% QD compared with triamcinolone will be carried out using the Bonferroni-Holm procedure at an overall 2-sided $\alpha = 0.03$ level.
- **Step 3:** If both of the null hypotheses in Step 2 are rejected, then a superiority test of INCB018424 1.5% QD compared with triamcinolone will be carried out at a 2-sided $\alpha = 0.03$ level.

If all 4 tests in Branch 1 are significant, then the overall level ($\alpha = 0.03$) of Branch 1 will be reallocated to Branch 2, and the first alternative hypothesis in Branch 2 will be tested with start level of 2-sided 0.05. If 1 or more of the tests in Branch 1 is nonsignificant, there will be no level reallocated from Branch 1 to Branch 2, and the first alternative hypothesis in Branch 2 will be tested with start level of 2-sided 0.02.

9.2.1.2.2. Tests in Branch 2

- Alternative hypotheses (superiority of INCB018424 1.5% QD and 0.5% QD compared with vehicle) will be tested in sequence using the alpha level decided in the previous steps.

If 1 or more of the 4 tests in Branch 1 is nonsignificant, but all tests in Branch 2 are significant, then the alpha level will be reallocated to Branch 1, and Branch 1 will reopen with a start level of 0.05.

9.2.2. Noninferiority Margin

In the historical study ([Beck et al 2014](#)), the difference of percentage change from baseline to Day 29 in EASI scores between active control (placebo and glucocorticoids) and placebo was 27.1% with the derived lower limit of 95% confidence interval (CI) 16.4%. Therefore, 27% constitutes the minimum expected benefit of triamcinolone (active control) over vehicle. Given that the result is based on 2 studies with small sample sizes, the margin is chosen to be -10%, which is between a half of the lower 95% CI (-8%) and 50% of the minimum effect (-13.5%).

Noninferiority analysis will be performed between each of the active treatment groups and triamcinolone.

9.2.3. Power Analysis

Given the assumptions specified in [Table 5](#), a simulation following the graphical procedure was performed and showed that a sample size of 50 subjects in each group would yield a power of > 99% to test the superiority of the each of the active treatment group (INCB018424 1.5% BID, INCB018424 1.5% QD, and INCB018424 0.5% QD) to the vehicle group with a 2-sample t test.

Assuming no true difference between the active treatment group and triamcinolone with respect to percentage change from baseline in EASI scores and an SD of 13%, the simulation showed that the sample size of 50 in each group would yield a power of > 99% to declare that the active treatment changes in INCB018424 1.5% BID and INCB018424 1.5% QD are noninferior to triamcinolone (ie, that the lower limit of the 2-sided 95% CI of INCB018424 minus triamcinolone is greater than or equal to the noninferiority margin of -10%). The sample size will also provide at least 95% power to test the superiority of each of the active treatment groups of INCB018424 1.5% BID and INCB018424 1.5% QD to the triamcinolone group.

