9.3. Level of Significance

A graphical procedure with a gatekeeping testing strategy for the primary and key secondary analyses will be implemented to control the overall Type I error rate at a 2-sided alpha level of 0.05. The underlying procedure is derived using the methodology developed in Bretz et al [\(2009\)](#). This method will guarantee a strong control of the family-wise error rate.

Simulations results are provided to illustrate Type I error control for the graphical procedure. The Type I error rates, provided in [Appendix E, Table E.2](#), are strongly controlled in all scenarios.

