APPENDIX E. STATISTICAL CONSIDERATIONS

Type I Error Rates

Six scenarios are examined for Type I error rates, corresponding to null hypothesis that there is no different treatment effect between 1 or more active treatment groups with active control or vehicle.

With 50 subjects per group, normal distributions, with standard deviation of 0.13, and mean percentage changes specified in [Table E.1](#) were generated. For each scenario, 10,000 replications were run using SAS® 9.2. Comparisons between each of the active dose to active control or vehicle are performed using 2 sample t-tests. Confidence intervals of the means (INCB018424 - active control or vehicle) were created with corresponding alpha level following the graphical procedure specified in [Section 9.2](#). The lower limits of CIs were compared with the critical values (0 for superiority, and -10% for noninferiority) for treatment comparisons. To provide conservative estimates, the primary comparison (INCB018424 1.5% BID vs vehicle superiority) was excluded from the procedure, that is, only key secondary endpoints were evaluated.

The Type I error rates are provided in [Table E.2](#) under different null hypotheses. The rates are compared with the nominal alpha 2.5%, which showed that the Type I error rates are well-controlled in all scenarios (< 2.5%).

Table E.1: Assumed Percentage Change From Baseline of EASI Score at Week 4 for Type I Error Rates

Scenario	1.5% BID	1.5% QD	0.5% QD	Active Control	Vehicle
S1	40%	40%	40%	50%	40%
S2	50%	40%	40%	50%	40%
S3	60%	40%	40%	50%	40%
S4	40%	40%	40%	50%	30%
S5	50%	40%	40%	50%	30%
S6	60%	40%	40%	50%	30%

Table E.2: 1-Sided Type I Error Rates (%)

Scenarios	S1	S2	S3	S4	S5	S6
Reject at least 1 hypothesis in	T11, T12, T13, T14, or T21 or T22	T12, T13, T14, or T21 or T22	T13, T14, or T21 or T22	T11, T12, T13, or T14	T12, T13, or T14	T13 or T14
Type I error rates	2.44	2.14	2.19	2.34	1.25	1.34

Note: T11: To test whether INCB018424 1.5% BID is noninferior to triamcinolone (active control).

T12: To test whether INCB018424 1.5% BID is superior to triamcinolone (active control).

T13: To test whether INCB018424 1.5% QD is noninferior to triamcinolone (active control).

T14: To test whether INCB018424 1.5% QD is superior to vehicle.

T21: To test whether INCB018424 1.5% QD is superior to vehicle.

T22: To test whether INCB018424 0.5% QD is superior to vehicle.

S1 to S6 are defined in [Table E.1](#).

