7.4.1. Efficacy Analysis for Key Secondary Endpoints

The efficacy analysis for key secondary endpoints includes the 6 comparisons if the primary null hypothesis is rejected. Each comparison will be analyzed using a similar MMRM to that specified for the primary analysis. The graphical approach as specified in [Figure 1](#) will be used to control the FWER.

Four tests for superiority of 1 of the INCB018424 doses to active control or vehicle cream will be performed using the least squares mean estimate of the percentage change from baseline in EASI at Week 4 from the MMRM model specified above. Superiority will be established if the p-value of the difference (INCB018424 minus the reference group, either active control or vehicle) is less than the alpha level determined by the graphical procedure.

For noninferiority, tests comparing each of 2 INCB018424 treatment groups (1.5% BID and 1.5% QD) to the active control group will be performed using the least squares mean estimate of the percentage change from baseline in EASI at Week 4. Noninferiority will be established if the lower limit of a 2-sided CI for the difference (INCB018424 minus active control) is higher than or equal to -10%. The level of the corresponding CI will be determined by the graphical procedure. In addition, a CI with the usual 95% level will be reported.

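### The >99% noninferiority power in Protocol 9.2.3 does not follow from its own inputs: they give about 97% per arm, and no alpha the graph can assign reaches 99%.

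*Protocol*

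**What the plan says.** Protocol 9.2.3 gives two sets of power figures. Superiority is evaluated under the Table 5 means. Noninferiority is evaluated under no true difference from triamcinolone, with SD 13%: "the simulation showed that the sample size of 50 in each group would yield a power of > 99% to declare" both 1.5% regimens noninferior. The criterion is spelled out: "the lower limit of the 2-sided 95% CI of INCB018424 minus triamcinolone is greater than or equal to the noninferiority margin of -10"%.

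The level for these tests is set elsewhere. Protocol 9.3 uses the graph "to control the overall Type I error rate at a 2-sided alpha level of 0.05". Under 9.2.1.1 and 9.2.1.2, Branch 1 starts with three-fifths of that, so BID noninferiority is tested at 0.03. QD noninferiority follows only if that succeeds, paired with BID superiority and "carried out using the Bonferroni-Holm procedure at an overall 2-sided" 0.03. Branch 1 can be retested at 0.05 under this condition: "If 1 or more of the 4 tests in Branch 1 is nonsignificant, but all tests in Branch 2 are significant". SAP 3.2.2 repeats these rules. On the transfer weights, 9.2.1.1 says: "The weights of the level to be passed on if 1 hypothesis is rejected are specified in" Figure 3, which is not in the text available to us. SAP 7.4.1 says of the noninferiority interval: "The level of the corresponding CI will be determined by the graphical procedure"; a 95% CI is reported in addition.

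Appendix E simulates one-sided Type I error for the six secondary tests, "which showed that the Type I error rates are well-controlled in all scenarios".

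**The concern.** The noninferiority power statement supplies every input needed to check it, and the check fails. BID noninferiority to triamcinolone is the entry test for Branch 1, which carries the key secondary objective. A reader of 9.2.3 would put the chance of missing noninferiority, when the drugs are equal, below 1%. On the stated inputs it is at least about 3% per arm, and higher for QD, which has to pass through BID and then a Holm pair. A failed noninferiority test would be read against the wrong background.

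The reopening rule accounts for part of the QD shortfall, so it matters that the text and the Appendix E simulation do not seem to use the same one.

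**Working it through.** **Inputs.** SD 13 points (Protocol 9.2); n = 50 per group, true difference 0, margin -10 points, 2-sided 95% CI (9.2.3); two-sample t tests (9.2.3 and Appendix E); overall 2-sided alpha 0.05 (9.3); starting level 0.03 for Branch 1 (9.2.1.2). No dropout is allowed for.

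**The stated figure.**

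- SE of the difference = 13 × √(2/50) = 2.6 points.
- Distance from truth to margin = 10/2.6 = 3.846 SE.
- Normal approximation: Φ(3.846 − 1.960) = Φ(1.886) = 97.0%.
- Noncentral t, df = 98, noncentrality 3.846: 96.8%.

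The stated value is above 99%, so it is not reproduced.

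**Could another alpha rescue it?**

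| 2-sided alpha | Power (t) |
|---|---|
| 0.05 (ceiling of the graph) | 96.8% |
| 0.03 (Step 1) | 94.8% |
| 0.015 (first Holm level, Step 2) | 91.2% |
| 0.10 (i.e. 1-sided 5%) | 98.5% |

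Reaching 99% would need a 2-sided alpha of about 0.13. Because no test can exceed 0.05, the weights in the missing Figure 3 do not matter here. For scale only, 99% at 0.05 would need 64 per arm, or an SD of at most 11.5%.

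**Could another event explain it?** Both arms noninferior at plain 95% CIs: about 94%. At least one of the two: 99.3%. Under the Table 5 means (+25 and +15 points over triamcinolone): about 100%. Either of the last two could be the source, but neither is what 9.2.3 describes. The superiority powers in 9.2.3 do reproduce under Table 5.

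**Through the written graph.** Simulation with 400,000 replicates, two-sample t tests and the primary gate applied; vehicle 30%, 0.5% QD 50% and triamcinolone 50%, as in Table 5.

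| Scenario | Branch 1 reopening | BID noninferior | QD noninferior |
|---|---|---|---|
| Both 1.5% arms = 50% | As written (any Branch 1 failure) | 96.8% | 91.7% |
| Both 1.5% arms = 50% | Only if the BID noninferiority test failed | 96.8% | 89.4% |
| Both 1.5% arms = 50% | None | 94.8% | 87.9% |
| BID 75%, QD 50% | As written | about 100% | 96.8% |
| BID 75%, QD 50% | Either of the other two | about 100% | 94.8% |
| Table 5 (BID 75%, QD 65%) | Any | about 100% | about 100% |

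**Which reopening rule did Appendix E use?** The six Table E.1 scenarios were re-run with the primary test excluded, as Appendix E specifies. T14 is read as QD superiority to triamcinolone. The table note defines it as superiority to vehicle, which duplicates T21 and would be a true effect in S4 to S6, so it could not count as a Type I error there. One-sided rates, %:

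| | S1 | S2 | S3 | S4 | S5 | S6 |
|---|---|---|---|---|---|---|
| Table E.2 | 2.44 | 2.14 | 2.19 | 2.34 | 1.25 | 1.34 |
| As written | 2.48 | 2.32 | 2.32 | 2.38 | 2.22 | 2.39 |
| Only if T11 failed | 2.48 | 2.32 | 2.32 | 2.38 | 1.42 | 1.45 |
| None | 2.48 | 2.32 | 2.32 | 1.51 | 1.42 | 1.45 |

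With 10,000 replicates, the Monte Carlo SE at 2.22% is √(0.0222 × 0.9778/10,000) = 0.147 points, so S5 lies (2.22 − 1.25)/0.147 = 6.6 SE from the written rule. S6 lies 6.9 SE away. The narrower rule fits all six entries to about 1.4 SE. No reopening fails at S4.

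**The case against.** The arithmetic is not disputed; the case on the other side is about weight.

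- **Size.** At the stated CI the gap is about 2 points on a power that stays near 97%. The sample size was justified first by the safety database, and under Table 5 nothing is underpowered. This stands, and it limits the consequence. It does not make the stated figure right.
- **CI level.** The 95% CI in 9.2.3 explains a power scenario and is not an analysis rule. SAP 7.4.1 is clear about what governs and also promises a 95% CI. This mostly stands: the analysis itself is not ambiguous. The power sentence still describes a different criterion from the test that will be run.
- **QD at 88% to 92%.** This needs both 1.5% arms equal to triamcinolone, a joint scenario that 9.2.3 does not fully specify. If BID keeps its Table 5 effect, QD is at 95% to 97%. That is fair, and the figures should carry their assumptions.
- **Reopening.** Table E.2 cannot identify the rule that was used. Retesting only T11 at 0.05, with the later steps kept at 0.03, gives practically the same six rates, and so would a coding shortcut. Figure 3 is unseen, and Protocol 9.2.1.2 and SAP 3.2.2 agree with each other. All of this stands. What remains is that S5 and S6 are incompatible with the written rule on the only sensible reading of T14.

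**Conclusion.** The concern holds. On the inputs in 9.2.3, noninferiority power is 96.8% per arm. The chance of a miss is therefore about 3% instead of under 1%, and no level available in the graph brings power to 99%. This part rests only on the protocol's own figures and does not depend on Figure 3.

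The graph-based QD figures (88% to 92%, or 95% to 97% if BID has its Table 5 effect) rest on the assumed means and on the reopening rule. The mismatch between the written reopening rule and Table E.2 is firm for S5 and S6; which rule was actually simulated is inference.

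The consequences are limited. All re-run one-sided Type I error rates stay below 2.5% under every rule tried, and margin, sample size and primary test are untouched. This should be fixed, but it is not a design flaw.

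**What to change.** 1. In Protocol 9.2.3, replace the noninferiority power with about 97% per arm at the 2-sided 95% CI under no true difference.
2. Add the power through the graph, naming the scenario and the reopening rule: for QD, about 88% to 92% if both 1.5% arms equal triamcinolone, and about 95% to 97% if BID has its Table 5 mean.
3. Say in 9.2.3 that the operative CI level is the one the graph assigns, as in SAP 7.4.1, with the 95% CI as an additional report.
4. State one Branch 1 reopening rule, identical in Protocol 9.2.1.2, SAP 3.2.2, Figure 3 and Appendix E. Correct the T14 definition in the Table E.2 note. If the written rule stands, re-run Table E.2.

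The cost is a few sentences, a check of the rule and at most one simulation re-run. No additional subjects are needed, and the margin and error control do not change.
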